#### 9.12 Discontinuation/Withdrawal of Participants from Study

The parent/ legal guardian has the right to withdraw their infant from the study at any time without having to provide a reason for doing so. In addition, the investigator may discontinue a participant from the study at any time if the investigator considers it necessary for any reason including:

- Ineligibility (either arising during the study or retrospective having been undisclosed at screening)

- Significant protocol deviation
- Significant non-compliance with treatment regimen or study requirements
- An adverse event, which requires discontinuation of the study medication or results in inability to continue to comply with study procedures.
- Lost to follow up- this will be declared when 3 attempts to contact by phone/email at different times of the day have been unsuccessful and a letter has been sent to the address with no reply within 2 weeks
- Participants who are withdrawn will not be replaced but data collected prior to discontinuation or withdrawal may still be used for analysis. The reason for withdrawal will be recorded in the source document and eCRF. If the participant is withdrawn due to an adverse event, the investigator will arrange for follow-up visits or telephone calls until the adverse event has resolved or stabilised. If a participant were to withdraw early, his/her GP and the Child Health Computer Department will be informed of any vaccinations that have been given, as well as outstanding routine immunisations.

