It will be left to the investigator's clinical judgment whether or not an AE is of sufficient severity to require the participant's removal from the study. A parent/ legal guardian may also voluntarily withdraw their child due to what he or she perceives as an intolerable AE.

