# Analysis for primary endpoint

The primary statistical analysis will be carried out on the basis of modified intention-to-treat (mITT). That is, participants who have received two doses of the vaccine will be included in the analysis. We will endeavour to obtain full follow-up on every participant to allow full mITT analysis, but we will inevitably experience the problem of missing data due to withdrawal and loss to follow-up.

The primary outcome is PT-specific antibody GMC concentration at 13 months of age. The GMC of PT-specific antibody will be compared between wP and aP under the hypothesis:

H0: GMCwP / GMCaP = 1 or 
$$log_{10}$$
GMCwP -  $log_{10}$ GMCaP = 0;

H1: GMCwP / GMCaP 
$$\neq$$
 1 or  $log_{10}$ GMCwP -  $log_{10}$ GMCaP  $\neq$  0.

The antibody concentration will be transferred using logarithmic transformations (base 10) to render a normal distribution. We will test the above hypothesis using mixed effects model, adjusting for pre-specified covariates. Estimates of PT-specific antibody concentration with the corresponding 95% confidence intervals (CI) will be delivered from the model at 13 months to compare the antibody response after an aP booster between the wP and aP groups. Interactions with time of blood samples will be included in the models for each comparison as appropriate (e.g. time x Bp vaccination). The results from the trial will be presented as comparative summary statistics (difference in  $log_{10}$ GMC) with 95% CIs, which will be calculated as the mean of  $log_{10}$ GMC in wP group compared with that in aP group.

An unstructured correlation matrix will be used to model the within-participant error correlation structure. We will also perform various sensitivity analyses using other imputation methods, e.g. multiple imputation and pattern mixture model, to test whether the results are robust to different assumptions about the missing data. The study results will be reported in accordance with the CONSORT (Consolidated Standards of Reporting Trials) 2010 statements.

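### Protocol 9.12 and 13.3.1 let unblinded staff remove an infant from the whole study when vaccine is stopped or the protocol is breached; this sits badly with the follow-up aim in 14.1

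*Protocol*

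**What the plan says.** Section 9.12 describes one kind of exit: "the investigator may discontinue a participant from the study at any time if the investigator considers it necessary for any reason including" a list of grounds. Three of these matter here: "Significant protocol deviation", "Significant non-compliance with treatment regimen or study requirements" and "An adverse event, which requires discontinuation of the study medication or results in inability to continue to comply with study procedures". Section 13.3.1 leaves to clinical judgment "whether or not an AE is of sufficient severity to require the participant's removal from the study".

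After removal, 9.12 provides three things: "data collected prior to discontinuation or withdrawal may still be used for analysis"; if the reason was an adverse event, "the investigator will arrange for follow-up visits or telephone calls until the adverse event has resolved or stabilised"; and notice to the GP and child health department about vaccines given and outstanding. It mentions no further study bleeds.

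Section 14.1 (analysis for primary endpoint) makes mITT the primary analysis, defined by receipt of two doses. It says: "We will endeavour to obtain full follow-up on every participant to allow full mITT analysis". The same sentence accepts that withdrawal and loss to follow-up will leave data missing. A mixed model is the primary method, with multiple imputation and pattern-mixture sensitivity analyses and a secondary per-protocol analysis.

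**The concern.** Stopping a vaccine, breaching the protocol and leaving follow-up are three different events. The first two may change what an infant receives or whether the infant counts as per-protocol. Neither is in itself a reason to stop measuring an infant who belongs to the primary analysis set. Because 9.12 and 13.3.1 offer only removal from the study, a decision about vaccine or compliance can also end sampling.

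The trial is open label (9.4), so whoever decides on removal knows the arm, and the background section and 9.11 expect wP to be the more reactogenic vaccine. Removals could therefore differ between arms. The planned imputation and pattern-mixture analyses can explore such losses only under assumptions; a sample actually taken needs none.

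Safety follow-up may shorten too. Section 13.3.2 ties SAE reporting to the participant's last visit, although 13.4 refers to the end of the study. Section 13.2.2 makes confirmed pertussis an SAE because of the reduced schedule.

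**Working it through.** **1. Which infants are affected.** I read the two doses in 14.1 as the priming doses at V1 and V3. An infant whose vaccine is stopped after dose 1 is not in the mITT set, so the point concerns removals after V3.

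**2. What those infants lose.** Table 1 (section 7.2) schedules blood at V1, V5, V6 and V7. No vaccine is given at V5 (9.5.5). At V6 blood is taken at step 6 and the booster given at step 8 (9.5.6). V7 is the primary 13-month bleed (9.5.7).

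| Infant removed after dose 2 | V5 (5 m) | V6 (12 m) | V7 (13 m) |
|---|---|---|---|
| Further vaccine stopped, no booster | avoidable loss | avoidable loss | not a post-booster value even if taken |
| Deviator who would still be boosted | avoidable loss | avoidable loss | avoidable loss of the primary value |
| Cannot comply with procedures | probably lost anyway | probably lost anyway | probably lost anyway |

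Removal after V5 spares the V5 sample. Removal before V5 leaves only the V1 value, taken before any study vaccine. The mixed model then has no post-vaccination value for that infant. V5 and V6 serve secondary endpoints and also inform the model about a missing V7.

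**3. The plan's own figure (7.1.2).** Inputs: SD 0.324 on the log10 scale; difference log10(135/80) = 0.2272; two-sided 5%; 90 analysed, so 45 per arm; 20% withdrawal. Two-sample t-test power (noncentral t) is 90.83%, against 90.8% stated. Inflation: 45/0.80 = 56.25, rounded up to 57 per arm, which agrees.

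**4. Precision.** The allowance is 57 − 45 = 12 losses per arm. Removals within it do not take power below plan. Beyond it, with the same SD and difference:

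| Analysed per arm | Power |
|---|---|
| 45 | 90.8% |
| 44 | 90.2% |
| 43 | 89.5% |
| 42 | 88.8% |
| 40 | 87.2% |

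Five losses per arm beyond the allowance would cost 90.8 − 87.2 = 3.6 points.

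**5. Bias, as assumption only.** Let a fraction q of wP infants be removed, with a mean s SDs above the arm mean. The observed wP mean then shifts by −q/(1 − q) × s × 0.324.

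- q = 5%, s = 0.5: −(0.05/0.95) × 0.5 × 0.324 = −0.0085, a GMC ratio multiplied by 0.98; 0.0085/0.2272 is about 4% of the planned difference.
- q = 10%, s = 1: −(0.10/0.90) × 1 × 0.324 = −0.036, a ratio multiplied by 0.92; 0.036/0.2272 is about 16%.

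If the removed infants lie below the arm mean, the shifts have the same size and the opposite sign. Neither q nor s is in the protocol. The formula is also for a complete-case mean, and the planned mixed model would give a different figure.

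**The case against.** The other side has a good deal right, and it rules out several stronger readings that a reader might infer.

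- **That 9.12 forces removal.** It does not. The investigator may remove an infant if it is considered necessary, and deviation and non-compliance must be significant. However, the open-ended list of reasons means that word does not really bound the discretion.
- **That 9.12 contradicts 14.1.** It does not. Section 14.1 states an effort, expects losses and plans sensitivity analyses, and 7.1.2 sizes the trial for 20% withdrawal.
- **That wP reactions after dose 2 will stop wP and deplete that arm.** No wP dose remains after V3; the next pertussis dose is the aP booster, the same in both arms. The background section also says hypotonic-hyporesponsive episodes typically follow the first dose. The route to arm-dependent loss is therefore narrower than it looks, though discretionary removal by unblinded staff remains.
- **That every lost V7 bleed is a lost primary value.** The primary objective is the response after the booster. An unboosted V7 value is a different quantity, and adding it without a rule could distort the mITT mean.
- **That a definite bias can be quoted.** The necessary inputs are absent and the sign is unknown.
- **That samples from withdrawn infants are barred from use.** The wording on earlier data is permissive, 9.13 ends the study only when all samples have been analysed, and the consent pages are not in the copy reviewed. The text does not support that complaint.

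What survives all this is that no section separates stopping vaccine from leaving the study, and none provides for bleeds that could still be taken.

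**Conclusion.** The point holds as a cheap, worthwhile improvement. For two-dose infants, 9.12 and 13.3.1 permit losses that the mITT analysis in 14.1 would rather avoid: V5 and V6 for any removed infant who could still be bled, and the primary 13-month value for deviators who would still have received the booster. This rests on the step order at V5 to V7 and on reading two doses as the priming doses.

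Its size cannot be derived from the protocol. On precision it is small: nothing within the planned allowance, and 3.6 points of power for five extra losses per arm. On bias, the assumed cases above give shifts of roughly 0.01 to 0.04 on the log10 scale in either direction; they are illustrations, not estimates.

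**What to change.** Reconcile 9.12 and 13.3.1 with 14.1 as follows.

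1. Define discontinuation of study vaccine and withdrawal from the study as separate events, each recorded with its reason.
2. State that a deviation or non-compliance by itself affects per-protocol membership, not follow-up. Narrow the open-ended grounds in 9.12 to match; deleting the two listed grounds alone would change nothing while any reason is still allowed.
3. Keep already scheduled sampling and SAE collection for infants who stop vaccine or deviate, unless the parent withdraws or the investigator judges further procedures unsafe.
4. State how a 13-month value from an infant who did not receive the booster is handled in the primary analysis, since it is not a post-booster response.

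Whether a vaccine is stopped remains the investigator's decision, and no clinical rule is proposed. The cost is an amendment to the wording, attendance by a few infants at visits already in the schedule, and some values from infants with deviations, which the secondary per-protocol analysis can set aside.

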#### 9.13. Definition of End of Study

The end of study defined as the when laboratory analysis of samples for primary and secondary end-points has been completed for all biological samples.

#### **10 INTERVENTIONS**

Vaccine products to be used	Commercial name_	IMP/non-IMP
DTaP-IPV-Hib- Hep B	Infanrix hexa ® (GSK)	IMP
DTwP- Hib-Hep B	Comvac 5 ® (Bharat Biotech)	IMP

#### Periscope AWARE Protocol version 4.1 dated 08-Dec-2023

IPV	Imovax ® polio (Sanofi Pasteur Ltd)	IMP
PCV 13	Prevenar 13 ® (Pfizer Ltd)	IMP
Men B	Bexsero ® (GSK)	non-IMP
Men C	Neisvac ® (Pfizer Ltd)	non-IMP
Rota	Rotarix ® (GSK	non-IMP
MMR	Priorix ® (GSK) or M-M-RVAXPRO ® (Merck,Shar	p and Dohme) UK
		non-IMP

#### 10.1 Study vaccines

The following vaccines will be used in this study:

#### Investigational products:

• DTaP-IPV-Hib- Hep B: Infanrix hexa ® (GSK): is diphtheria (D), tetanus (T), pertussis (acellular component) (Pa), hepatitis B (rDNA) (HBV), poliomyelitis (inactivated (IPV) and *Haemophilus influenza* type b (Hib) conjugated vaccine (adsorbed). The vaccine contains 3 *Bordetella pertussis* antigens: Pertussis Toxoid (PT), filamentous Haemagglutinin (FHA) and pertactin (PRN). The vaccine is indicated for primary and booster to prevent diseases described above and is licensed to be used in the European Union, in children between 6 weeks and 36 months of age. Infanrix-hexa will be administered intramuscular as a 2-dose primary (2 and 4 months) and a booster at 12 months of age as described in the SMPC section 4.2. Infanrix-hexa will also be used as a booster at 12 months for the children primed with DTwP-Hib-Hep B an immovax-IPV. The vaccine will be purchased commercially in single dose prefilled syringe and a vial containing Hib powder, preparation will be done according to section 6.6 of the SmpC.

• **DTwP-Hib-Hep B:** Comvac 5 ® (Bharat Biotech) diphtheria (D), tetanus (T), pertussis (whole cell) (w), hepatitis B (rDNA) (HBV), and *Haemophilus influenza* type b (Hib) conjugated vaccine (adsorbed). Will be given intramuscular as a 2-dose primary (2 and 4 months).

- IPV: Imovax ® polio (Sanofi Pasteur Ltd): Inactivated poliomyelitis vaccine, containing 3 types of the poliovirus: type 1 (Mahoney), type 2 (MEF1) and type 3 (Saukett). Is indicated for infants from 2 months of age, children and adults for both primary and booster doses. This vaccine is licensed in 60 countries including France and Finland. Imovax-polio will be given intramuscular as a 2-dose primary (2 and 4 months). The vaccine will be purchased commercially in single dose prefilled syringes, preparation will be done according to section 6.6 of the SmpC
- PCV13: Prevenar13® (Pfizer Limited): a pneumococcal conjugate vaccine that contains 13 different pneumococcal serotypes (1, 3, 4, 5, 6A, 6B, 7F, 9V, 14, 18C, 19A, 19F and 23F) and is licensed in Europe. It is part of the UK routine schedule at 2, 4 and 12 months of age. This vaccine is only going to be administered at 2, 4 and 12 months of age

Non- Investigational products:

The routine NIP vaccines are not part of this study, but will be given to all infants in the study by the study team for practical reasons.

- **Men B:** Bexsero® (Novartis): a meningococcal serogroup B vaccine adsorbed rDNA vaccine. This vaccine is licensed in Europe and currently given as part of the UK routine schedule (2, 4 and 12 months).
- Men C: Neisvac-C ® (Pfizer Ltd): Meningococcal Group C Polysaccharide Conjugated Vaccine adsorbed. Is recommended for active immunisation in children from 2 months of age, adolescents and adults for prevention of the *Neisseria meningitidis* serogroup C disease and is licensed in Europe. MenC is currently part of the UK immunization schedule at 12 months of age (Menitorix: MenC and Hib combined vaccine). We intend to administer the monovalent MenC vaccine (Neisvac-C ®) because the Hib component is contained in infanrix-hexa.
- Rotavirus: Rotarix® (GSK): a live attenuated vaccine (RIX4414 strain) that is administered orally as a suspension in a pre-filled oral applicator. It protects against gastroenteritis caused by rotavirus. This vaccine is licensed and is part of UK routine schedule at 2 and 3 months. This vaccine is only going to be administered at 2 and 4 months of age

MMR: Priorix® (GSK): a live attenuated vaccine that protects against measles (Schwarz strain), mumps (RIT 4385 strain) and rubella (Wistar RA 27/3 strain) or M-M-RVAXPRO® (Merck,Sharp and Dohme) UK. Is indicated for active immunisation in children more than 9 months of age, adolescents and adults, to prevent the diseases above described. This vaccine is licensed in Europe and is given in the UK as part of the routine schedule at 12 months and 3 ½ years of age. This vaccine is going to be administered in UK at 13 months of age

Where needles are not supplied with the vaccine a 25mm, 23 gauge (0.6mm) needle will be used.

## **10.2 Storage of IMP and other vaccinations**

The IMP and other vaccines on the trial will be stored at the study site following the manufactured recommendation and as per existing SOPs. Vaccines will be shipped at +2°C to +8°C to the study site. Upon receipt at the study site, vaccines will be immediately transferred to a +2°C to +8°C to +8°C temperature monitored refrigerator for storage.

The refrigerator will be secure and have controlled access. Cool boxes with an attached thermometer will be used while transporting the study treatment during scheduled visits.

The temperature of the refrigerator is remotely monitored and the site will be informed of any excursions in temperature. In case of temperature deviations, the study vaccines cannot be used and should be quarantined until authorisation to use the vaccine is received from the manufacturers.

#### **10.3 Compliance with Trial Treatment**

All vaccines will be administered by study staff during the visits therefore compliance will not be an issue.

## **10.4 Accountability of the Trial Treatment**

The study vaccine (Comvac 5®) will be manufactured and sourced from Bharat Biotech, based in India.

Other study vaccines will be purchased commercially and distributed to the study sites through OTC Direct (http://www.otcdirectltd.co.uk/) or obtained as part of the usual supply from the respective national immunisation programs.

A vaccine accountability log will be used to check that supplies used and remaining vaccine numbers matched at all times. All used packaging and any unused or damaged vaccines will be destroyed locally at the end of the study depending on the manufacturer's instructions.

## 11. OTHER NON-INVESTIGATIONAL PRODUCTS

All infants will be offered local anaesthetic cream to numb the skin before venepuncture.

#### 11.1 Name and description of non-investigational product(s)

A local anaesthetic cream (EMLA®/ AMETOP®) will be applied for an appropriate period of time prior to each venepuncture. Written instructions about how the cream should be applied will be given and explained to the parents/guardians.

EMLA 5%® contains Lidocaine 2.5% w/w (25 mg/g) and Prilocaine 2.5% w/w (25 mg/), with marketing authorisation number PL 39699/0088, first approved 16th May 1996 and renewaled on 5th of July 2002.

AMETOP® contains Tetracaine base 4.0% w/w with marketing authorisation number PL 14038/0001 on 09/10/2006.

EMLA® will be the first anaesthetic cream to be supplied to the parents for this population, that can be replaced by AMETOP® in case of previous or new allergy to EMLA®. In order not to increase the length of the visit, the study team can also apply AMETOP® in case the parents/guardians didn't apply the cream before the beginning of the visit, considering that the time for action for AMETOP ® is less (30 minutes) than EMLA® (60 minutes).

#### 11.2 Summary of known and potential risks and benefits

Summary of known and potential risks and benefits can be found in the SmPC of each product.

## **12 LABORATORY**

#### 12.1 Sample collection

#### Blood samples collection:

Blood samples will be collected according to SOPs agreed across all Periscope partner sites and transported to the laboratory for further processing within 4 hours. Samples taken from the participant will be labelled with a participant, visit and site-specific number, according to the sample management plan.

#### Mucosal samples collection

Mucosal samples, from mucosal lining fluid (MLF) will be collected using synthetic absorptive matrices (MAP), according to SOPs agreed across all Periscope partner sites and transported to the laboratory until further testing.

#### Periscope AWARE Protocol version 4.1 dated 08-Dec-2023

	V1	V2	V3	V4	V5	V6	V7
	Baseline	Men B	Vaccines	Men B		Vaccines	Vaccines
	Vaccines	vaccine		vaccine			
	2 M	2M +7d	4M	4M+d7	5M	12M	13M
aP	4.0 mls				4.0 mls	6.0 mls	6.0 mls
wP	4.0 mls				4.0 mls	6.0 mls	6.0 mls
subgroups							

**Table 3:** Summary of the type of assays which may be undertaken according to visits and sub-groups

Indication of typical blood volumes required for proposed assays as an explanation of total volumes needed (S=serum; Bpc=Plasma cells T=T-cell assay; Bm=B-cell (memory); GEX: gene expression; Ef: Euroflow; CyT: CyTOF)

Serum : up to 1.0ml

Bm/Bpc : up to 3.0ml

**T-cell assay** : up to 3.0ml for whole blood assay and up to 6.0ml for 'in-depth' T-cell assay

**PBMC storage:** for exploratory assays (e.g. antibody repertoire, antigen-specific single-cell sorting)

Plasma, for use in some of the serological assays, will be collected from samples processed for cellular assays (e.g. B-cell, T-cell). For each time-point, in the event of lower volumes of blood being obtained than the maximal for that time-point, there will be a prioritisation of assays and the volumes to be used for each assay. The volumes stated above are an ideal volume to allow testing of the broadest array of antigens and phenotypes and a minimum volume will be defined to ensure that the primary and secondary end-points are achieved. This prioritisation will be stated clearly in the laboratory analysis plan.

#### 12.2 Sample processing

Samples will be received, processed and stored in the local laboratory for further distribution to the central PERISCOPE Consortium laboratory in batches. Samples will be labelled with a barcoded label including the participant number, study visit and study site. The codes will be provided by the Consortium for uniformisation and easy access to the samples.

Some assays will be undertaken within the local laboratory from fresh and stored samples. Samples of serum, plasma, mucosal lining fluid, cellular material, RNA and DNA not to be used at the local laboratory will be shipped for storage at the PERISCOPE consortium Biobank at Radboud University Medical Centre, [name], the Netherlands for subsequent use by investigators of the PERISCOPE consortium to address the primary, secondary and exploratory end-points of this study and also within the other studies of the Consortium. The laboratories that may be involved in these analyses are listed in Appendix A and B. These analyses will be according to a laboratory analysis plan, which will be developed as part of the study. Within PERISCOPE, a number of core assays will be developed in a standardized manner to allow comparison of immune responses to *B. pertussis* across the different clinical studies.

A more detailed analysis plan, including the PERISCOPE-wide strategy for biomarker identification, will be drafted by the Clinical Study Teams according to the Description of Action of the PERISCOPE consortium.

